9 CONDUCT OF THE STUDY

9.1 Scheduling of Study Procedures

Patients hospitalized for COVID-19 with a prior history of CVD or at least one risk factor for CVD will be screened.

Day 0-1 -- Baseline assessments and Randomization and start of study medication

The following evaluations will be performed a baseline:

- Written informed consent
- Clinical assessment
- Demographics
- Medical History/Current conditions, including prior CV events and interventions
- Concurrent medication and CV medication history for the previous 24 weeks
- C-SSRS
- Vital signs, including heart rate (HR), blood pressure, height and weight
- Chest X-ray
- 12-lead ECG, including QTc interval assessment
- LVEF by echocardiography
- Assessment of Ordinal Outcome Scale
- Local laboratory assessments, including CBC, AST/ALT, alkaline phosphatase, bilirubin, creatinine/eGFR, INR, serum pregnancy test (in women with child-bearing potential only), glucose, total cholesterol, lymphocyte count and LDH
- Retention of frozen samples for hs-troponin, NT-proBNP, D-dimer, hs-CRP, ferritin, TNF-alpha, IL-1 beta, IL-6, IL-10 and additional parameters of interest
- Retention of frozen samples for CBD levels

Randomization and start of study medication (2.5 mg/kg b.i.d.) in the evening of Day 1 after all baseline assessments have been completed and all eligibility criteria are met. Randomization must be no later than 96 hours after hospital admission. Patients awaiting planned admission to hospital in an emergency room for less than 96 hours can be screened and enrolled into the trial.

Day 3

- Vital signs, including HR and blood pressure
- 12-lead ECG, including QTc interval assessment 5 hours post morning dose (time window 3.5 – 6 hours)
- Assessment of Ordinal Outcome Scale
- AE and SAE recording
- Recording of changes in concomitant medications
- Study drug dose increase to 5.0 mg/kg b.i.d., if previous dose is well-tolerated
- Study drug accountability
- Retention of frozen samples for hs-troponin, NT-proBNP, D-dimer, hs-CRP, ferritin, TNF-alpha, IL-1 beta, IL-6, IL-10 and additional parameters of interest

- Retention of frozen samples for CBD levels

Day 5

- Vital signs, including HR and blood pressure
- 12-lead ECG, including QTc interval assessment 5 hours post morning dose (time window 3.5 – 6 hours)
- Assessment of Ordinal Outcome Scale
- AE and SAE recording
- Recording of changes in concomitant medications
- Study drug dose adjustment to 7.5 mg/kg b.i.d., if 5.0 mg/kg b.i.d. is well-tolerated (If 5.0 mg/kg b.i.d. is not tolerated, then dose decrease back to 2.5 mg/kg b.i.d.)
- Study drug accountability
- Retention of frozen samples for hs-troponin, NT-proBNP, d-dimer, hs-CRP, ferritin, TNF-alpha, IL-1 beta, IL-6, IL-10 and additional parameters of interest
- Retention of frozen samples for CBD levels

Day 7

- Clinical assessment
- Vital signs, including HR, blood pressure and weight
- 12-lead ECG, including QTc interval assessment 5 hours post morning dose (time window 3.5 – 6 hours)
- Assessment of Ordinal Outcome Scale
- AE and SAE recording
- Recording of changes in concomitant medications
- Study drug dose adjustment and accountability
- Local laboratory assessments, including CBC, AST/ALT, alkaline phosphatase, bilirubin, creatinine/eGFR, INR, lymphocyte count and LDH
- Retention of frozen samples for hs-troponin, NT-proBNP, D-dimer, hs-CRP, ferritin, TNF-alpha, IL-1 beta, IL-6, IL-10 and additional parameters of interest
- Retention of frozen samples for CBD levels

If the patient is discharged before Day 7, the assessments up to Day 7 will be carried out as out-patient or home visits. After Day 7, all remaining scheduled assessments will be carried out during out-patient visits.

Time windows for out-patient visits or home visits up to Day 7 are +/- 1 day; after Day 7, time windows are +/- 2 days.

Day 14

- Clinical assessment
- Vital signs, including HR, blood pressure and weight
- 12-lead ECG, including QTc interval assessment 5 hours post morning dose (time window 3.5 – 6 hours)
- Assessment of Ordinal Outcome Scale

- AE and SAE recording
- Recording of changes in concomitant medications
- Study drug dose adjustment and accountability
- Local laboratory assessments, including CBC, AST/ALT, alkaline phosphatase, bilirubin, creatinine/eGFR, INR, lymphocyte count and LDH

Day 21

- Clinical assessment
- Vital signs, including HR, blood pressure and weight
- 12-lead ECG, including QTc interval assessment 5 hours post morning dose (time window 3.5 – 6 hours)
- Assessment of Ordinal Outcome Scale
- AE and SAE recording
- Recording of changes in concomitant medications
- Study drug dose adjustment and accountability

Day 28

- Clinical assessment
- Vital signs, including HR, blood pressure and weight
- Chest X-ray
- 12-lead ECG, including QTc interval assessment 5 hours post morning dose (time window 3.5 – 6 hours)
- LVEF by echocardiography
- Assessment of Ordinal Outcome Scale
- CMR (subset of patients at selected sites)
- C-SSRS
- PICQ
- AE and SAE recording
- Recording of changes in concomitant medications
- Study drug accountability
- Local laboratory assessments, including CBC, AST/ALT, alkaline phosphatase, bilirubin, creatinine/eGFR, INR, lymphocyte count and LDH
- Retention of frozen samples for hs-troponin, NT-proBNP, D-dimer, hs-CRP, ferritin, TNF-alpha, IL-1 beta, IL-6, IL-10 and additional parameters of interest
- Retention of frozen samples for CBD levels

Day 45

- Clinical assessment
- Vital signs, including HR, blood pressure and weight
- Assessment of Ordinal Outcome Scale
- Recording of changes in concomitant medications
- AE and SAE recording
- CMR if not recorded on Day 28 (subset of patients at selected sites)

Day 60

- Clinical assessment
- Vital signs, including HR, blood pressure and weight
- PICQ
- Assessment of Ordinal Outcome Scale
- Recording of changes in concomitant medications
- AE and SAE recording

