4.2.3 Secondary Safety Endpoints

The secondary safety endpoints include changes in C-SSRS, blood chemistry and hematology parameters (including lymphocyte count), ALT, AST, bilirubin, eGFR, creatinine, INR and QTc interval from ECG recordings 5 hours post morning dose (time window 3.5 – 6 hours) during 28 days of study drug administration.

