6 STUDY DESIGN

6.1 Summary of Study Design

Multi-center, double-blind, randomized, placebo-controlled, parallel group design. 1:1 randomization.

Screening (Assessment Day 0-1): Patients hospitalized for COVID-19 will be screened. If patient consent can be obtained, baseline assessments will be carried out: Physical examination (including vital signs), ECG (including QTc interval assessment), echocardiography, chest X-ray, local laboratory assessments, including CBC, AST/ALT, alkaline phosphatase, bilirubin, creatinine/eGFR, INR, serum pregnancy test (in women with child-bearing potential only), glucose, total cholesterol, lymphocyte count and LDH. Frozen samples will be retained for central analysis of CardiolRx™ levels, hs-troponin, NT-proBNP, D-dimer as well as inflammatory markers (hs-CRP, ferritin, TNF-alpha, IL-1 beta IL-6, IL-10). A C-SSRS will also be completed.

If all eligibility criteria are met, the patient will be randomized to either CardiolRx™ or placebo.

Study treatment will be initiated in the evening of Day 1, after all baseline assessments have been completed and the patient is randomized. Study medication must be taken with food. The maximum dosing period of patients will be 28 days.

Oral administration is as follows:

Study Day	a.m. dose [mg/kg of body weight] CardiolRx™ or placebo	p.m. dose [mg/kg of body weight] CardiolRx™ or placebo
1	N/A	2.5
2	2.5	2.5
3	2.5	5
4	5	5
5	5	7.5
6 - 28	7.5	7.5

If the next higher dose is not tolerated, the dose will be reduced to the previous tolerated dose. The highest tolerated dose will be administered until Day 28.

At each study visit, drug accountability will be done. New bottles of study medication will be dispensed at each study visit (Days 3, 5, 7, 14 and 21).

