6.3 Follow-up procedures

After Day 7, routine assessments will be carried out on a weekly basis until Day 28.

On Day 28 the assessments include the following: Physical examination (including vital signs), ECG (recorded 5 hours post morning dose [time window 3.5 – 6 hours] for assessment of QTc interval), echocardiogram to measure LVEF, chest X-ray and local and central laboratory assessments, including CBC, AST/ALT, alkaline phosphatase, bilirubin, creatinine/eGFR, INR, lymphocyte count and LDH. In addition, a C-SSRS will be completed and the patient will be asked to answer a PICQ. A subset of patients at selected sites will also undergo a CMR assessment, either on Day 28 or 45.

Further follow-up visits are scheduled for Day 45 and Day 60 post randomization. These include a clinical assessment, including vital signs as well as the completion of the PICQ (at Day 60 only).

Changes in concomitant medications, AEs and SAEs will be recorded during all study visits after consent has been obtained.

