8 INVESTIGATIONAL PRODUCTS, DOSE AND DURATION OF TREATMENT

8.1 *Investigational Product*

CardiolRx™ is pharmaceutically produced. It contains cannabidiol in a concentration of 100 mg/ml and is free of tetrahydrocannabinol (THC; <5 ppm).

8.2 *Administration, Dosage and Duration of Treatment*

Study drug will be administered orally (via syringe)* with food according to the following treatment schedule:

Study Day	a.m. dose [mg/kg of body weight]	p.m. dose [mg/kg of body weight]
	CardiolRx™ or placebo	CardiolRx™ or placebo
1	N/A	2.5
2	2.5	2.5
3	2.5	5
4	5	5
5	5	7.5
6 - 28	7.5	7.5

At each study visit, drug accountability will be done. New bottles of study medication will be dispensed at each study visit (Days 3, 5, 7, 14 and 21).

If the next higher dose is not tolerated, the patient should return to the last tolerated dose. The highest tolerated dose will be administered until Day 28 (4 weeks post randomization).

The maximum treatment period will be 28 days.

* If the patient requires mechanical ventilation, the study medication is administered through a naso-gastric tube.

Justification for Dosing Regimen

COVID-19 is an acute illness with, at times, rapid progression of symptoms and signs. Because of this, it seems important to increase the blood level of the investigational agent as quickly as possible to achieve the potential anti-inflammatory and anti-cytokine actions that are likely to be important in this population. However, this agent has not been administered previously to this population, so care must be taken to observe closely for

adverse drug effects or drug-drug interactions that might have significant negative consequences. A similar product containing a highly purified botanical extract of CBD has been approved for use in pediatric epilepsy to a dose up to 10 mg/kg twice daily (Devinsky et al. 2016). We have chosen to restrict the maximum dose in this COVID-19 population to 7.5 mg/kg b.i.d. because of the expected elderly and perhaps frail condition of some of the enrolled patients. Investigators are encouraged to decrease the dose if there are indications of intolerance of a given dose to the previously tolerated dose.

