9.2.3 Standard 12-lead Electrocardiogram (ECG)

A 12-lead ECG will be performed at baseline, at Days 3, 5, 7, 14, 21, and 28 5 hours post morning dose (time window 3.5 – 6 hours).

The effect of CBD (CardiolRx™) on cardiomyocyte ion channel function has not been reported to date. One study assessed the effect of a product with equal THC and CBD content (Sativex) on QTc (Sellers et al. 2013). No effect was found. In the Abstracts of the 2017 meeting of the American Epilepsy Society, Van Landingham et al. from GW Pharmaceuticals presented the PK data for single normal and large doses of their CBD and assessed the impact on QTc (VanLandingham et al. 2017). No impact was identified. Another study of the effects of CBD on QT interval in children and young adults with epilepsy syndromes is listed on Clinical Trials.gov but was not completed because the investigator has been on medical leave and recruitment was difficult. Cardiol has contracted to have half-maximal inhibitory concentration (IC 50) values recorded for sodium, potassium and calcium channels in a human cardiac cell line. Until those results are available, the FDA has requested that the QTc intervals on repeated ECG recordings at the times of peak blood levels of CBD and its major metabolites are assessed after the morning dose of study medication. The time to peak blood level for CBD and its two major metabolites (7-hydroxy CBD and 7-Carboxy CBD) has been reported to be at approximately 4 hours after the dose has been taken (Tayo et al. 2020; Taylor et al. 2018). In our Phase I study the maximum concentration occurred at 5 hours post dose; this interval is specified for this protocol.

As noted in section 6.3 of the IB, there is considerable potential for drug-drug interactions (DDIs) in the patient population under study. Of particular concern is the potential for CBD to inhibit the metabolism of a drug(s) that has the ability to prolong the QTc interval. Therefore, if the QTc does increase after the institution of the study drug, the Investigator should consider this possibility, identify the concomitant medication responsible for it and adjust the dose of the medication as appropriate.

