Because of this concern, an electrocardiogram (ECG) will be recorded every other day for the first 7 days of drug dosing and on Days 14, 21 and 28; the recording should be done 5 hours after the morning dose of the study drug (time window 3.5 – 6 hours). The ECG will be assessed by the Investigator at the clinical site, the QT interval measured (the QTc calculated) and recorded in the case report form (CRF), with a copy of the ECG appended. The QT interval is measured from the beginning of the QRS complex to the end of the T wave and averaged over three cardiac cycles. The average QT interval should be corrected for heart rate variability using Bazett's formula ($QT_c = QT / \sqrt{RR}$) or Fridericia's formula ($QT_c = QT / RR^{1/3}$) to create the QTc interval. Each patient should have the QTc measured using the same method on all designated days in the study. If the QTc interval increases to 500 msec or more – or increases 60 msec or more from the baseline recording on any one measurement, this will be reported as an SAE and the study medication will be discontinued.

The QT interval can be obtained from the automated measurements of the ECG recorder, unless the data quality is poor. It is the corrected value that is to be recorded in the CRF.

After 100 patients have completed the Day 28 assessment (or terminated the study earlier), the QTc data will be analyzed (unblinded) by the DSMC. If an impact on the QTc interval by the study drug has been found, the DSMC will evaluate the appropriateness of continuing the trial.

The presence of a bundle branch block represents a particular challenge in properly measuring the QTc interval. Following international recommendations, QT interval should be measured in leads showing the longest QT interval, which is usually in right precordial leads. In presence of a BBB, these leads are strongest affected by conduction delay and therefore hamper adequate measurement. A new formula for evaluation of the QT interval in patients with left bundle branch block (LBBB) was introduced in 2014:

$$QT_{mean} = QT_{BBB} - 50\% QRS_{BBB} \text{ (Bogossian et al. 2014)}$$

This formula has proved to be a reliable tool in clinical practice for QTc interval evaluation in patients with LBBB, right bundle branch block (RBBB) or bifascicular block. (Bogossian et al. 2020; Erkacic et al. 2020)

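### The Day 28 visit window runs to Day 30, past the last scheduled dose, so a permitted Day 28 ECG can miss the post-dose timing in the QTc endpoint and still be tabulated as Day 28

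*Protocol*

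**What the plan says.** **Visit window.** After Day 7 all visits are out-patient, and Protocol Section 9.1 says that "after Day 7, time windows are +/- 2 days". Day 28 has no separate rule.

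**Dosing.** Treatment starts on the evening of Day 1. The last row of the dosing table covers Days 6 to 28, morning and evening. Section 6.1 adds "The maximum dosing period of patients will be 28 days", and Section 8.2 repeats the cap: "The maximum treatment period will be 28 days". Neither section extends dosing to the date on which the patient actually attends.

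**ECG timing.** The secondary safety endpoint in Section 4.2.3 is "QTc interval from ECG recordings 5 hours post morning dose", with a window of 3.5 to 6 hours, during the 28 days of drug administration. Section 6.3 applies the rule to Day 28 ("recorded 5 hours post morning dose"), and Section 9.2.3 states it again ("the recording should be done 5 hours after the morning dose of the study drug"). The stated reason is regulatory: "the FDA has requested that the QTc intervals on repeated ECG recordings at the times of peak blood levels" of CBD and its main metabolites be assessed.

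**SAP.** Section 4.2.2 keeps the 5-hour timing in the endpoint. Section 6.5 presents visit data under the nominal label from the eCRF, and Section 9.3.6 tabulates available ECGs by arm and visit. Neither checks the actual day or the time since the last dose.

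**The concern.** The general visit tolerance and the end of dosing were set separately, and they meet at Day 28. A site that sees the patient on Day 30 is inside the visit window, yet it cannot obtain the ECG that the endpoint describes. The reading is then taken after treatment has ended, but it enters the Day 28 row with on-dose readings and carries no mark.

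What is at stake is the meaning of that row. The ECGs are timed to catch QTc near peak drug level. If the drug does prolong QTc at peak, mixing in post-treatment readings from the active arm could make the Day 28 change look smaller than it is. The SAP already recognises that actual timing can matter: Section 9.2 uses actual rather than nominal times for the biomarker areas under the curve. It has no similar provision for QTc.

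**Working it through.** The plan states no figure to reproduce here. The check is calendar arithmetic on three rules.

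**Inputs**
- Visit window: +/- 2 days after Day 7, +/- 1 day up to Day 7 (Protocol 9.1).
- Last scheduled dose: evening of Day 28 (dosing table, 6.1 and 8.2).
- ECG window: 3.5 to 6 h after the morning dose (4.2.3, 9.1, 9.2.3).
- ECG days after baseline: 3, 5, 7, 14, 21, 28 (9.2.3).

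**Step 1: permitted days.** 28 - 2 = 26 and 28 + 2 = 30, so five days are allowed. By the dosing table, Days 29 and 30 (two of the five) have no morning dose. This counts calendar days, not patients.

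**Step 2: is Day 28 the only visit affected?** The latest permitted days for the other full-dose ECG visits are 7 + 1 = 8, 14 + 2 = 16 and 21 + 2 = 23. All are before Day 28. The window crosses the end of dosing only at the last ECG visit: one of six post-baseline readings, or one of the four scheduled at 7.5 mg/kg (Days 7, 14, 21, 28).

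**Step 3: how firm is Day 29?** Section 8.2 equates Day 28 with four weeks after randomization, and randomization is on Day 1 (Appendix 17.2.1). Four weeks after Day 1 is 1 + 28 = Day 29. Likewise, 28 full days from the evening of Day 1 run to the evening of Day 29 and would include that morning. The dosing table lists no such dose and is the more specific text, so Day 29 is off-dose by the table with slight ambiguity. Day 30 is off-dose on every reading.

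**Step 4: time since the last dose.** Clock times are not in the documents. Assume a last evening dose between 18:00 and 22:00 on Day 28 and an ECG between 09:00 and 17:00.

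| ECG day | Shortest gap | Longest gap |
|---|---|---|
| 29 | 22:00 to 09:00 = 11 h | 18:00 to 17:00 = 23 h |
| 30 | 11 + 24 = 35 h | 23 + 24 = 47 h |

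The shortest gap is 11 - 6 = 5 h beyond the upper limit of the ECG window.

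**Step 5: residual exposure.** Section 9.2.14.2 equates six half-lives with 18 days, so one half-life is 18/6 = 3 days = 72 h. On a single-exponential assumption, the fraction left after h hours is 0.5^(h/72). That gives 0.5^(11/72) = 0.90 at 11 h and 0.5^(47/72) = 0.64 at 47 h. The sum ignores the faster fall from peak, so it is indicative only. It suggests that a late reading is off-peak but not drug-free.

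**The case against.** **The rules can be read together.** The ECG rule is specific and the visit window is general. A site that follows both books the ECG on Days 26 to 28, and Section 14.4.1 requires exact adherence. A later ECG is then a deviation, and SAP Section 5.4 lists deviations. This stands in part: the rules are compatible, and a reader should not infer that the Day 28 ECG is impossible to perform as specified. But the window allows the later days, nothing warns the site, and a deviation listing does not change the Day 28 table.

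**There may be nothing to dilute.** Section 3.6 reports no adverse QTc effect in Phase I, and Section 9.2.3 cites two studies without one. Step 5 suggests that much of the drug remains. This stands as a limit on size. A reader might infer that the window hides a QTc signal; the documents do not show one.

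**The data safety committee.** Section 9.2.3 says "After 100 patients have completed the Day 28 assessment (or terminated the study earlier), the QTc data will be analyzed (unblinded) by the DSMC", which tempts the reader to conclude that this review was compromised. The documents do not support that. They do not say that the committee uses the SAP's nominal-visit table, its charter is not available here, and the study ended early with no statement that 100 patients were reached.

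**Excluding late readings would do harm.** This stands fully. Patients who stop drug remain in follow-up (Section 6.7.1), so off-dose ECGs can arise at any visit. A rule that simply removed them would also remove patients stopped for QTc prolongation, which is selection on the outcome of interest. A rule for Day 28 alone, or one that ignored readings before 3.5 h, would not enforce the endpoint's own definition either.

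**Conclusion.** The point holds as a minor design flaw. The visit window permits a Day 28 ECG on a day with no scheduled morning dose: certainly Day 30, and Day 29 by the dosing table. Such a reading falls outside the QTc endpoint's definition, and the SAP would report it as Day 28 without a mark.

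The size is limited. One of six post-baseline readings is exposed, Days 7, 14 and 21 give unaffected full-dose readings, and the SAP's ECG output is descriptive. The primary endpoint and the sample size are not touched. How many patients attended late is unknown. The hours in Step 4 rest on assumed clock times, but no plausible change to them brings a Day 30 reading within 6 h of a scheduled dose.

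**What to change.** **Protocol.** Give the Day 28 ECG its own window of -2/0 days and leave the other Day 28 assessments at +/- 2 days. This is one sentence and adds no procedure. The cost is that a patient who can attend only on Day 29 or 30 may need an earlier trip for the ECG. Because the study ended early, this now serves only as a lesson for a later protocol.

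**SAP.** This part can still be applied, since SAP Section 2 places approval before unblinding.
- Keep the planned table of all available ECGs.
- At every post-baseline visit, flag any ECG outside 3.5 to 6 h after a morning dose. If only dates were captured, flag any ECG taken after the patient's last dosing day.
- Report the number flagged per arm and visit.
- Add a display of in-window readings beside the full table, not in place of it, so that patients who stopped drug for QTc prolongation are not removed from view.
- Keep every reading in the listings and in the checks for QTc above 500 msec or a rise above 60 msec.

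The cost is one extra display and a derived flag. The full flag needs dose and ECG times. The eCRF is not available here, so whether those times were captured cannot be confirmed; the date-based version works without them.
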